### 9.2 Sample Size Calculations

---

This is a confirmatory Design Validation clinical investigation where the calculated sample size is sufficient to test the primary and secondary hypotheses described in Section 9.1.

#### 9.2.1 Primary Hypothesis

Table 3 below shows the sample size estimations for a paired t-test ( $\alpha = 0.05$ ) in order to detect differences in mean ocular comfort scores between Test vs. Control conditions. Assuming a standard deviation of a paired difference of 13 points, a sample size of 44 subjects provides adequate power to detect a potential paired difference of 7 points on a 0-100 point scale.

**Table 3: Sample size estimation (0-100 numerical scale)**

n=20		Paired Difference		
		5	7.5	10
S.D. (Paired difference)	8	76%	98%	99%
	10	56%	89%	99%
	12	42%	76%	94%
	15	29%	56%	81%

### **9.2.2 Secondary Hypothesis**

Assuming a standard deviation of a paired difference of 0.1 logMAR, a sample size of 27 subjects provides adequate power to detect a potential paired difference of 0.05 logMAR in mean vision scores between Test vs. Control conditions for a paired t-test (alpha = 0.05).

Therefore, a sample size of approximately 45 completing subjects is sufficient for this study.

## **9.3 Statistical Analysis**

---

Summary statistics [may/will] be produced (e.g. mean, standard deviation). Paired t-test will be used to compare slit lamp biomicroscopy, lens fit and subjective scores between study lens types. Where applicable, Repeated Measures Analysis of Variance (ANOVA) or paired analysis will be used to compare the variables between study visits. The critical alpha level for statistical significance will be set at  $p \leq 0.05$ , with adjustment for multiple comparisons.

Equivalence testing will be undertaken to first determine statistical non-inferiority and then equivalence (if applicable) to the comparator (Control) lens, to confirm the primary and secondary hypotheses.

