## 1 Study Objective

---

This is a confirmatory Design Validation study to provide supportive evidence to demonstrate that the [REDACTED] lens meets the clinical performance requirements specified in the User Requirements Design Inputs per D28298, DHF0122.

Specifically, the User Requirements to be evaluated in this clinical study are:

- Vision of [REDACTED] is equivalent to [REDACTED]
- Comfort of [REDACTED] is equivalent (or better) to [REDACTED]
- Lens fit of [REDACTED] is equivalent to [REDACTED]
- Lens handling of [REDACTED] is equivalent to [REDACTED]
- Ocular health of [REDACTED] is equivalent to [REDACTED]

Details of the statistical hypothesis that are required to be met in fulfilment of Validation can be found in Section 9.1 below.

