### 9.1 Statistical Hypothesis

---

The primary statistical hypothesis is that the comfort performance with the Test lens will demonstrate statistical equivalence to the comparator (Control) lens over two days of lens wear.

The secondary statistical hypothesis is that the vision performance with the Test lens will demonstrate statistical equivalence to the comparator (Control) lens over two days of lens wear.

*Other hypotheses:*

The lens fit performance with the Test lens will demonstrate statistical equivalence to the comparator (Control) lens over two days of lens wear.

The lens handling performance with the Test lens will demonstrate statistical equivalence to the comparator (Control) lens over two days of lens wear.

Corneal staining performance with the Test lens will demonstrate statistical equivalence to the comparator (Control) lens over two days of lens wear.

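### Fit, handling and corneal staining are equivalence hypotheses in Section 9.1, but on those labels Section 9.3 gives them only tests for a difference, which cannot show equivalence

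*Combined protocol and SAP*

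**What the plan says.** Section 1 lists five User Requirements (vision, comfort, fit, handling, ocular health). Each is to be equivalent to Control, except that comfort "is equivalent (or better) to" Control. It then says: "Details of the statistical hypothesis that are required to be met in fulfilment of Validation can be found in Section 9.1 below".

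Section 9.1 makes comfort the primary hypothesis and vision the single secondary one. Under "Other hypotheses" it places three more: fit, handling and staining. The one on staining reads: "Corneal staining performance with the Test lens will demonstrate statistical equivalence to the comparator (Control) lens over two days of lens wear". Those on fit and handling follow the same pattern.

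Section 9.3 names the comparison between lenses: "Paired t-test will be used to compare slit lamp biomicroscopy, lens fit and subjective scores between study lens types". It adds repeated measures ANOVA or paired analysis between visits, and a 0.05 significance level adjusted for multiple comparisons. Equivalence testing, with non-inferiority first, is planned "to confirm the primary and secondary hypotheses".

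Section 9.2 refers to the same pair of hypotheses as described in 9.1, and 9.2.2, on the secondary hypothesis, deals with vision alone. The synopsis and Section 7.1, however, list vision, fit, handling and anterior ocular health together as secondary.

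**The concern.** A paired t-test takes no difference as its null hypothesis. A significant result shows a difference. A non-significant result shows only that none was detected, which can happen because the sample is small or the measure noisy. Neither result demonstrates that the lenses differ by less than an acceptable amount.

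On the 9.1 labels, three of the five hypotheses tied to Validation therefore have no test that could confirm them. The plan does not say that a non-significant t-test meets a requirement, but it names no other result for these three. The report would then have to choose a rule, a variable and a margin after the data are in, in a study described as confirmatory.

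**Working it through.** **1. The sections side by side**

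| Hypothesis | Label in 9.1 | Label in synopsis and 7.1 | Equivalence test in 9.3, on 9.1 labels | Stated margin |
|---|---|---|---|---|
| Comfort | Primary | Primary | Yes | None (7 points is a difference to detect, 9.2.1) |
| Vision | Secondary | Secondary | Yes | None (0.05 logMAR is a difference to detect, 9.2.2) |
| Lens fit | Other | Secondary | No | None |
| Handling | Other | Secondary | No | None |
| Corneal staining | Other | Secondary (as anterior ocular health) | No | None |

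No single variable is named either. Fit is recorded on six items at dispensing and at follow-up of each pair (7.5.2 to 7.5.4). Handling at follow-up has two overall scales plus 3 × 3 = 9 five-point items.

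**2. The plan's own power figures.** Take T as noncentral t with n − 1 degrees of freedom and noncentrality d√n/SD. Power is P(|T| > t for 0.975). With n = 20 and differences of 5, 7.5 and 10:

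| SD | Table 3 (%) | Recomputed (%) |
|---|---|---|
| 8 | 76 / 98 / 99 | 75.5 / 97.8 / 100 |
| 10 | 56 / 89 / 99 | 56.5 / 88.9 / 98.9 |
| 12 | 42 / 76 / 94 | 42.4 / 75.5 / 94.2 |
| 15 | 29 / 56 / 81 | 29.4 / 56.5 / 80.7 |

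Table 3 is thus a two-sided test for a difference. For comfort with n = 44, the noncentrality is 7√44/13 = 3.57 and power is 93.7%. No power is given for fit, handling or staining.

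**3. The two rules for fit, handling and staining.** From the plan: n = 45 completers (9.2.2) and alpha 0.05 (9.3). The plan gives no SD or margin for these endpoints, so the margin is an assumption, shown over a range in SDs of the paired difference.

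- Difference test: non-significant when |T| ≤ t(0.975, 44 df) = 2.015, with noncentrality δ√45 for a true shift of δ SDs.
- Two one-sided tests (TOST) at one-sided 0.05: pass when |mean difference| + 1.680 × s/√45 is below the margin, so that the 90% confidence interval lies inside it. The pass probability comes from integrating over the sample SD.

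| Margin (SD) | Noncentrality if true shift = margin | t-test non-significant, shift = margin | TOST pass, shift = margin | TOST power, true difference 0 |
|---|---|---|---|---|
| 0.30 | 2.01 | 49.7% | 4.0% | 26.5% |
| 0.40 | 2.68 | 25.3% | 5.0% | 68.1% |
| 0.443 | 2.97 | 17.2% | 5.0% | 80.0% |
| 0.498 | 3.34 | 9.6% | 5.0% | 90.0% |

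The non-significance rate falls to 5% at 0.55 SD. Beyond that, the t-test rejects a lens at the margin more often than TOST does. Simulation agreed at the points checked (0.3 SD non-significant 0.497; TOST at 0.4 SD 0.050).

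**4. Comfort, as a check on claimed harm.** Take SD 13, n = 45 and an illustrative margin of ±7. The standard error is 13/√45 = 1.94. A lens 5 points worse is non-significant 28.7% of the time and passes TOST 26.5% of the time, so the rules barely differ there. A lens 5 points better passes TOST 26.5% of the time but passes non-inferiority about 100% of the time.

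**The case against.** The strongest reply is that 9.3 may use the word secondary as the synopsis and 7.1 do. Section 4 also says the design was chosen to demonstrate equivalence, without limiting this to two endpoints. On that reading all five hypotheses get equivalence testing and the fault is inconsistent labelling. The reading is possible but weaker. Section 9.3 speaks of hypotheses, 9.1 defines a single secondary hypothesis, and 9.2 points to 9.1 and sizes vision alone. Even if it were accepted, no equivalence test could be run without a variable and a margin.

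Second, 9.3 also plans repeated measures ANOVA. That is true, but it too tests for differences.

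Third, the error rates are hypothetical: they need a misreading that the plan does not state, and assumed margins. This stands. The figures illustrate the consequence; they do not measure this trial's error.

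Four practical points also stand and are taken into the fix:

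- Section 1 requires ocular health, while 9.1 narrows it to corneal staining.
- Testing without adjustment contradicts the adjustment sentence in 9.3.
- Joint power is lower than power per test.
- Staining is graded, and the text available does not show the scale, so a mean-based test may suit it poorly.

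**Conclusion.** The concern holds. Taking the labels in 9.1, three hypotheses that Section 1 ties to Validation have only difference tests, which cannot support the conclusion required of them. If 9.3 meant the labels in 7.1, the sections conflict and the three still lack a variable and a margin.

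The size cannot be fixed from the documents. With 45 completers, reading non-significance as equivalence would be much too lenient at margins of 0.3 to 0.4 SD, moderately lenient at 0.44 to 0.50 SD, and stricter than TOST at the margin above about 0.55 SD. These rates assume normally distributed paired differences. The primary comfort hypothesis does have equivalence testing planned, and no harm is claimed there from the t-test. The point should be settled before unmasking, but it does not undermine the primary analysis.

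**What to change.** In Section 9.3, with matching edits elsewhere:

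1. Extend the non-inferiority-then-equivalence testing to fit, handling and staining. For each, name one variable and visit (for example the 100-point handling score at follow-up) and compare the 90% confidence interval of Test minus Control with a margin the sponsor fixes before unmasking. Check that the method suits the staining grade, and say whether staining stands for the ocular health requirement in Section 1.
2. State margins for comfort and vision, and say whether 7 points and 0.05 logMAR are those margins.
3. Keep non-inferiority first, and reconcile Section 1 with 9.1 on comfort so that a more comfortable Test lens does not fail.
4. State that a non-significant paired t-test does not support equivalence.
5. Use one set of secondary and other labels in the synopsis, 7.1, 9.1 and 9.3.
6. If the sponsor confirms that every hypothesis must be met, run each equivalence test at one-sided 0.05 without adjustment and amend the multiple-comparison sentence to match. Splitting alpha as 0.05/3 would cut power at a 0.50 SD margin from 90% to 75%.

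Alternatively, if the three are not formal requirements, say so in Section 1 and 9.1.

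The cost is wording, up to five margins (three if 7 points and 0.05 logMAR are adopted) and a few confidence intervals. No extra subjects or visits are needed if the margins are about 0.44 to 0.50 SD (80% to 90% power per test at no true difference); tighter margins cost power. Requiring all three also lowers the chance of passing: if the tests were independent, 0.80³ = 51% or 0.90³ = 73%, and more with positive correlation. A formal test may fail.

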## **4 Justification for the Study Design**

---

The Apollo lens has successfully passed the preclinical biocompatibility tests as identified in the risk assessment document. Preliminary safety and clinical performance of the [REDACTED] lens have been evaluated in one feasibility clinical study. This study is summarized in the Investigator Brochure (IB).

A two-day crossover study is sufficient to validate the clinical performance of the lens against the User Requirements. A crossover design has been chosen since it minimizes the impact of potential sympathetic effects between the two eyes (e.g. an uncomfortable lens in one eye may impact the subjective rating of the fellow eye). The study contact lenses do not alter the physiology of the eye and hence there is no carryover effect requiring a washout period. The order effect will be tested.

The choice of comparator product was made in order to assess the clinical performance against a currently marketed product representative of generally accepted state of the art.

The choice of study design was made to demonstrate statistical equivalence to the comparator (Control) lens over two days of lens wear. A sample size determination was made of sufficient magnitude so as to be able to adequately test the primary statistical hypothesis, and is shown in Section 9.2.

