## 7.3 Subjects

---

A maximum of 50 subjects will be enrolled in this study in order for approximately 45 to complete the study. Each subject will be given a unique ID number. ID numbers will not be re-used. All subjects must meet the study inclusion and exclusion criteria listed below.

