### 7.4.2 Randomization procedures

In this crossover study design, each subject will wear the Test lens or the Control lens first in a bilateral fashion followed by the alternate lens. The order of lenses will be determined by a predetermined randomization schedule.

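### Section 9.3 compares the lenses without a period term and names no model for the deciding equivalence test; a 2x2 crossover model is a cheap, small improvement

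*Combined protocol and SAP*

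**What the plan says.** Section 7.4.2 fixes the design feature that matters here: "The order of lenses will be determined by a predetermined randomization schedule". The allocation ratio and any blocking are not stated. Section 7.3 adds "A maximum of 50 subjects will be enrolled in this study in order for approximately 45 to complete the study".

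Section 9.3 gives the between-lens analysis: "Paired t-test will be used to compare slit lamp biomicroscopy, lens fit and subjective scores between study lens types". Visual acuity is not in that list; only the sample-size text in 9.2.2 ties a paired t-test to it. For comparisons between visits, 9.3 says "Where applicable, Repeated Measures Analysis of Variance (ANOVA) or paired analysis will be used to compare the variables between study visits". In a separate paragraph it says "Equivalence testing will be undertaken to first determine statistical non-inferiority and then equivalence (if applicable) to the comparator (Control) lens", as the means of confirming the primary and secondary hypotheses. No model, interval or margin is given there.

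Section 4 says of carryover "hence there is no carryover effect requiring a washout period", and then "The order effect will be tested". Section 9 does not return to order.

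**The concern.** In a two-period crossover each lens difference within a subject contains the period difference, with opposite sign in the two orders. A paired t-test ignores order. A period effect therefore inflates its variance estimate and, if the completed orders are unequal, shifts its mean. A model with a period term removes both.

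The carryover argument in section 4 does not exclude a period effect, and conditions do differ between periods. Pair 1 is fitted on eyes that have been lens-free for at least 12 hours (7.3.1). Pair 2 is fitted at a visit for which subjects are asked to have worn Pair 1 for at least 3 hours (7.5.3). This makes a period effect possible but says nothing about its size.

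At stake is the interval behind the equivalence decision. If it is built from the unadjusted paired difference, it may be wider than it needs to be. A test of order with no stated consequence also leaves the choice of analysis open until the data are seen.

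**Working it through.** **The plan's own figure.** Section 9.2.1: "Assuming a standard deviation of a paired difference of 13 points, a sample size of 44 subjects provides adequate power" for a 7-point difference. The noncentrality is 7/(13/√44) = 3.57. A two-sided 5% paired t-test on 43 df then has power 93.7%. The plan states no power figure to compare with this.

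**Inputs.** From the documents: SD 13 (9.2.1) and 45 completers (7.3). Assumed, because the documents are silent: margin ±7 (the planning difference), 90% interval, true lens difference 0, orders 23/22, and period effects π of 2 and 5 points.

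**Set-up.** Let d = Test − Control, τ the lens effect, and π the period 2 mean minus the period 1 mean. The mean of d is τ + π in the order Control–Test (n1 subjects) and τ − π in the order Test–Control (n2 subjects).

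- Paired analysis: expected estimate τ + π(n1 − n2)/N, with N − 1 = 44 df. Its expected variance estimate is multiplied by 1 + 4π²n1n2/[N(N − 1)SD²], where SD is the within-sequence SD.
- Crossover model: the estimate is half the sum of the two sequence means, with the pooled within-sequence SD and N − 2 = 43 df. It does not depend on π.

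**Variance and width at 23/22, SD 13 within sequence.**

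- π = 2: 1 + 4·4·506/(45·44·169) = 1.024. Mean 90% interval width is 6.55 versus 6.48 points (about 1% wider).
- π = 5: 1 + 4·25·506/(45·44·169) = 1.151. Width is 6.95 versus 6.48 (about 7% wider).
- Bias at π = 5 is 5 × 1/45 = 0.11 point.

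**Equivalence power, by simulation** (error about 0.1 percentage point):

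| Reading of SD 13 | π | Paired | Crossover model |
|---|---|---|---|
| Total SD; within-sequence √(169 − 4) = 12.85 | 2 | 94.6% | 94.9% |
| Total SD; within-sequence √(169 − 25) = 12.0 | 5 | 96.1% | 97.3% |
| Within-sequence SD | 2 | 94.1% | 94.4% |
| Within-sequence SD | 5 | 92.5–92.6% | 94.4% |
| Within-sequence SD | 10 | 85.4% | 94.4% |

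**Loss in terms of subjects (within-sequence reading, π = 5).** With no period effect, 42 completers give 92.6% power and 39 give 90.3%. The 5-point power loss is therefore like losing about 3 of 45 completers. The width comparison gives a larger number, 45 × (1 − 1/1.151) = 5.9, but it overstates the cost in power. A period effect inflates the estimated standard error and leaves the true sampling error of the paired mean unchanged, whereas losing subjects inflates both.

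**False pass** (true difference at −7, nominal 5%). The crossover model gives 4.9–5.1% throughout. The paired analysis gives:

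| Completed orders | π | Paired |
|---|---|---|
| 23/22 | 2 | 5.0% |
| 23/22 | 5 | 4.4% |
| 22/23 | 5 | 3.5% |
| 25/20, bias toward zero | 5 | 6.9% |
| 27/18, bias toward zero | 5 | 10.6% |
| 18/27, bias away from zero | 5 | 1.2% |
| Averaged over unrestricted 1:1 allocation | 2 or 5 | 5.0% |

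The 27/18 bias is 5 × 9/45 = 1.0 point.

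**Range (23/22, within-sequence SD 13).**

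- Margin ±5: 61.8% versus 62.8% at π = 2, and 56.0% versus 62.9% at π = 5.
- Margin ±10: 99.9% for both methods.
- Margin ±7 with a 95% interval: 87.9% versus 88.4% at π = 2, and 84.6% versus 88.4% at π = 5.

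**The case against.** The case for leaving 9.3 alone is substantial. With near-balanced orders the paired analysis keeps its error rate at or below about 5%. The wording of 9.2.1, an SD of a paired difference, most naturally means the total SD, which already contains any period variance; on that reading the plan meets its intended power. A 5-point period effect is 5/7 = 71% of the planning difference, and nothing in the documents suggests one so large in adapted wearers under masking. Order is partly handled: section 4 promises a test, and the between-visit analysis in 9.3 could serve as a period assessment. The equivalence model is unstated, so an unadjusted interval is an inference. The margin moves power far more (about 62% at ±5, 99.9% at ±10) than the period term does.

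All of this stands as to size. It does not remove the gap: the named lens comparison has no period term, and neither the order test nor the visit comparison adjusts the lens interval.

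A reader might infer that the plan inflates the chance of falsely declaring equivalence. The documents do not support that. It needs clearly unequal completed orders together with a sizeable period effect in the unfavourable direction. A 27/18 split cannot arise from 25/25 allocation with five losses. Under unrestricted 1:1 allocation, a split at least that uneven in a given direction has probability 11.6%, and the false-pass rate averaged over such allocation stays at 5.0%.

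**Conclusion.** The point holds as a low-priority, inexpensive improvement. Section 9.3 omits a period term from the lens comparison and names no model for the test that decides the study. The expected consequence is a mildly conservative analysis. On the plain reading of the SD, the crossover model gains 0.3 percentage points of equivalence power at a 2-point period effect and 1.2 at 5 points, with no shortfall against plan. On the within-sequence reading the gain is about 0.3 and 1.9 points.

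These figures rest on an assumed ±7 margin, a 90% interval, 23/22 completers and assumed period effects, none of which the documents give. The 10-point and 27/18 results are stress cases only. Two further inferences should be avoided: that the plan ignores order, which section 4 contradicts, and that the study is underpowered for want of a period term, which the figures do not show.

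**What to change.** In 9.3, for comfort, logMAR acuity and other approximately continuous scores, replace the paired t-test with a 2x2 crossover model: lens, period and sequence as fixed effects, subject as random. State that the non-inferiority/equivalence interval is taken from this model. Report its period estimate as the order assessment promised in section 4. Coarse slit-lamp and fit grades were not examined here and need not change on this account.

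The cost is two sentences and analysis code, with no new data. Statistically it is one degree of freedom when orders are balanced (94.4% power either way at 23/22 with no period effect). If orders are unequal and there is no period effect, there is also a small power loss: 94.4% to 93.4% at 27/18, and about 94.4% to 93.8% averaged over unrestricted allocation. Under unrestricted allocation there is no net gain until the period effect exceeds about 2 points.

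This change does not supply the missing margin or interval level, which the equivalence decision needs whatever model is used.

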## **9.4 Data Entry / Data Management**

---

Data collection is the responsibility of the clinical trial staff at the site under the supervision of the clinical site Principal Investigator. The Principal Investigator is responsible for ensuring the accuracy, completeness, legibility, and timeliness of the data reported. All source documents should be completed in a neat, legible manner to ensure accurate interpretation of data.

The clinical data for this study may be entered by designated study site personnel onto paper or electronic case report forms (CRFs). Case history and symptoms questionnaires may be given to subjects to complete in paper or electronic form.

Unless otherwise documented, the CRFs will be considered the source document.

The Sponsor or Sponsor's representatives will be authorized to gain access to the source documentation for the purposes of monitoring and auditing the study.

If study information is collected using an automated piece of equipment, the information may be recorded directly from the instrument display, captured electronically as output, or printed and entered into the CRF. The CRF will become the source document if there is no printout.

